#### 6.2.3 Post-Entry Evaluations

Post-entry evaluations occur after the study entry visit and vaccination #1 administration at week 0. Study visits are scheduled as indicated in the SOE.

The visit window for the post-entry evaluations is  $\pm 14$  days.

Due to the feasibility challenges posed by the COVID-19 situation, starting 03/16/20, the visit window is broadened from  $\pm 14$  days to -14 days to +60 days. The broadened visit window is applicable to visits scheduled to occur before 04/30/20. This will be reviewed again at a later date to see if the 04/30/20 date should be extended (to include visits occurring after 04/30/20), and/or if the visit windows themselves need to be extended further. **See the update below.**

**Upon further review, the visit window is broadened from  $\pm 14$  days to -14 days to +180 days for visits that were planned to occur before 07/15/20. While +180 days is allowed, sites are encouraged to schedule the applicable visits within +90 days.**

The week 24 and week 26 visits should remain separate and coordinated to be as close to 2 weeks apart as feasible, but can be up to 60 days apart. Thus, if the week 26 visit has to be delayed, it is better to postpone the week 24 visit until the week 26 visit can occur 2 weeks later, or as close to that interval as possible.

NOTE A: The deferred study vaccinations #2, #3, and #4 should be performed within 14 days from the time of the previously scheduled week 4, week 12, and week 24 visits, respectively (see [section 6.3.10](#)).

NOTE B: After study entry, administration of non-HIV vaccines must occur more than 2 weeks prior to the scheduled study vaccination #2 (week 4), #3 (week 12), and #4 (week 24) injections.

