4.1 Analysis Populations

Modified Intent-To-Treat (mITT): All randomized participants who have been exposed to study treatment (i.e., at least one dose of study drug).

Per-Protocol (PP): All eligible, randomized participants who 1) received all four study vaccination / placebo administrations, and 2) did not take any medication prohibited by the study protocol on or prior to their week 26 visit (as defined per protocol section 10.7.1).

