4.3 Visit Schedule and Analysis Windows

The schedule of evaluations is given in Section 6.1 the protocol. See timing of evaluations below:

- **Screening:** evaluations must be completed within 60 days prior to randomization (i.e., entry, week 0) unless otherwise specified.
- **Pre-Entry:** evaluations must be completed at least 24 hours after screening evaluations have been completed and at least 24 hours prior to entry evaluations unless otherwise specified.
- **Entry (week 0):** evaluations must occur at least 24 hours after pre-entry evaluations unless otherwise specified. Study entry or baseline is defined as the randomization date. The value used for baseline summaries will be the last evaluation on or before the randomization date. Participants must begin treatment within 72 hours after study enrollment.
- **Post-Entry:** evaluations occur after the study entry visit and vaccination #1 administration at week 0. The visit window for the post-entry evaluations is \pm 14 days.

- **Week 4** (vaccine #2 administration): weeks (2, 6]
- **Week 12** (vaccine #3 administration): weeks (10, 14]
- **Week 24** (vaccine #4 administration): weeks [22, 26]
- **Week 48**: evaluations will be completed at the participant's final on study visit and scheduled within a ± 14 days; weeks (46, 50].

Due to the delayed visits during the COVID-19 pandemic, starting 03/16/20, the visit window for week 24 and 48 was broadened from ±14 days to -14 days to +60 days. The broadened visit window was applicable to visits scheduled to occur before 04/30/20. Upon further review, the visit window was then broadened from ±14 days to -14 days to +180 days for visits that were planned to occur before 07/15/20. While +180 days was allowed, sites were still encouraged to schedule the applicable visits within +90 days. Thus, the new visit window for week 24 is weeks [22, 50] and week 48 is weeks [46, 74]

According to CM # 2, the week 24 and week 26 visits should remain separate and coordinated to be as close to 2 weeks apart as feasible, but can be up to 60 days apart. Thus, if the week 26 visit has to be delayed, it is better to postpone the week 24 visit until the week 26 visit can occur 2 weeks later, or as close to that interval as possible.

- Any deferred study vaccinations #2, #3, and #4 should be performed within 14 days from the time of the previously scheduled week 4, week 12, and week 24 visits, respectively.
- **Discontinuation Evaluations:**

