 - Participants who are enrolled, but who do not receive vaccination #1 will be taken off study. No further evaluations are required. These participants will be replaced.
 - Premature Treatment Discontinuation Evaluations: Participants who prematurely discontinue study treatment prior to receiving vaccination #2 or #3 should remain on study (off study treatment) until the final visit. No further vaccinations should be administered. The participants should complete the premature treatment/study discontinuation valuation as specified in the SOE. Participants should complete the safety evaluations per protocol until study completion (clinical assessments, hematology, chemistries and VRC review).
 - Premature Study Discontinuation Evaluation: Participants who discontinue the study prior to the final visit should complete the premature treatment/study discontinuation evaluations as specified in the SOE.

The analysis windows will be formed around each study visit using the midpoints between adjacent weeks as cutoffs. If there are multiple evaluations within the window for a given visit, then the evaluation closest to the scheduled study week will be used, and the earlier measurement will be used if there are two measurements which are equally distant from the scheduled week.

5 Statistical Methods

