5.1 Analysis of the Primary Immunogenicity Objective

The planned analysis will compare $Y = \text{sum of CEs recognized by CD4 and CD8 T cells at week 26 minus the number at baseline}$ between the p24CE/full-length Gag DNA and placebo arm, using a two-sided 5% level Wilcoxon rank-sum test, which is anticipated to have greater statistical power than analyzing the binary version of whether $Y > 0$, for which statistical power was based.

An exact 95% confidence interval (CI) for the median of all paired differences between observations in the two arms (i.e., Hodges-Lehmann estimate) will be calculated to provide additional insight on the effect of p24CE/full-length Gag DNA vaccine. Comparisons will also be made between the Gag DNA alone vaccine arm and each of the other arms in the same manner.

The primary immunogenicity analysis for this pilot study will be per protocol, limited to participants who received all four study vaccination/placebo administrations and who did not take any medication prohibited by the study protocol on or prior to their week 26 visit. Since the amount of missing data is expected to be low in this study, the primary comparison will be based on the complete case analysis, i.e., remove records with missing data.

The following sensitivity analyses will be carried out to measure the robustness of the study findings:

- Using the stratified Wilcoxon (Van Elteren) test adjusting for the stratification factor.
- Using modified ITT approach for the primary comparison.
- Excluding the data from participants with delayed #2 and/or #3 vaccination injection due to the COVID -19 pandemic.

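### The COVID-19 sensitivity analysis in SAP 5.1 excludes delayed vaccinations #2 and #3 but not #4, the only vaccination visit for which SAP 4.3 states a broadened window

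*SAP*

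**What the plan says.** SAP 5.1 lists three sensitivity analyses for the primary immunogenicity comparison. The third is the only one that deals with the pandemic: "Excluding the data from participants with delayed #2 and/or #3 vaccination injection due to the COVID -19 pandemic". It sets no minimum length of delay.

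SAP 4.3 says that "the visit window for week 24 and 48 was broadened from ±14 days to -14 days to +60 days", later extended to +180 days for visits planned before 07/15/20. It then gives new windows of weeks [22, 50] for week 24 and [46, 74] for week 48. Vaccination #4 is given at week 24, and no vaccine is given at week 48. Weeks 4 and 12 (#2 and #3) are listed with (2, 6] and (10, 14], with no broadened version.

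Protocol 6.2.3 words the broadening for post-entry visits in general. It adds that if week 26 must be delayed, "it is better to postpone the week 24 visit until the week 26 visit can occur 2 weeks later", or as near to that as possible, with at most 60 days between the two visits. SAP 4.3 repeats this.

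SAP 4.3 also says: "Any deferred study vaccinations #2, #3, and #4 should be performed within 14 days" of the scheduled visit.

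The per-protocol set in SAP 4.1, used for the primary analysis, requires that participants "received all four study vaccination / placebo administrations". Neither SAP 4.1 nor SAP 5.1 states a timing condition.

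**The concern.** The check is there to show whether pandemic dosing delay drives the result. As written, it leaves out the dose for which the SAP itself describes a delay, which is also the last boost before the primary sample.

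Moving week 24 together with week 26 protects the interval from #4 to the sample, but it lengthens the interval from #3 to #4. Participants with that changed schedule and no other delay are in the primary set and also in the set meant to test it. If the two results agree, a report could claim robustness to COVID-19 dosing delay when only #2 and #3 delays were examined.

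**Working it through.** **1. The plan's own windows.** The +180-day rule gives 24 + 180/7 = 49.7, rounded to week 50, and 48 + 180/7 = 73.7, rounded to week 74. The lower limits are 24 − 2 = 22 and 48 − 2 = 46. Both windows in SAP 4.3 reproduce.

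**2. Who is removed.** Take participants who received all four doses, took no prohibited medication, have a baseline and week 26 value, and had one dose delayed by the pandemic.

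| Delayed dose | Primary per-protocol set | mITT sensitivity set | COVID-19 sensitivity set |
|---|---|---|---|
| #2 only | kept | kept | excluded |
| #3 only | kept | kept | excluded |
| #4 only | kept | kept | **kept** |

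No analysis in SAP 5.1 removes the third row.

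**3. How late #4 could be with a usable week 26 value.** Scheduled days are #3 = 84, #4 = 168 and week 26 = 182. The planned #3-to-#4 gap is 168 − 84 = 84 days. Under ±14 days its maximum is 182 − 70 = 112 days.

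SAP 4.3 states: "The analysis windows will be formed around each study visit using the midpoints between adjacent weeks as cutoffs". A sample after the upper cutoff gives no week 26 value and drops out, because "the primary comparison will be based on the complete case analysis". The schedule of evaluations is not in the text available, so the next visit after week 26 has to be assumed:

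- Next visit week 48: cutoff (26 + 48)/2 = week 37 = day 259.
- Next visit week 36: cutoff (26 + 36)/2 = week 31 = day 217.
- Next visit week 30: cutoff (26 + 30)/2 = week 28 = day 196.

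The latest day for #4 is the cutoff minus the #4-to-sample interval. Days late are that day minus 168. The gap is that day minus 84, with #3 on schedule.

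| Assumption | Latest #4 | Days late | #3-to-#4 gap |
|---|---|---|---|
| Week 48 next, 14 days to sample | 259 − 14 = 245 | 77 | 161 |
| Week 48 next, 60 days to sample | 259 − 60 = 199 | 31 | 115 |
| Week 36 next, 14 days to sample | 217 − 14 = 203 | 35 | 119 |
| Week 30 next, 14 days to sample | 196 − 14 = 182 | 14 | 98 |
| 14-day deferral rule governs | 168 + 14 = 182 | 14 | 98 |
| [22, 50] window overrides the midpoint rule | 168 + 180 = 348 | 180 | 264 |

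If #3 was given 14 days early (day 70), each gap is 14 days longer; the first row becomes 175.

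**4. Weight of one participant.** Taking 10% off the planned arm sizes leaves 20 × 0.9 = 18 on p24CE and 10 × 0.9 = 9 on placebo. One participant is 1/18 = 5.6% or 1/9 = 11.1% of an arm.

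**The case against.** The best defence is that #4 was left out on purpose. A late #4 is within the broadened window and is paired with a moved week 26, so the time from last boost to sample is kept. A late #2 or #3 has no such pairing, and under SAP 4.3 a delay beyond their listed windows is out of window. This is coherent, but the SAP does not state it. It also does not deal with the longer #3-to-#4 gap, and up to 60 days between #4 and the sample is allowed. The documents give no reason to expect a longer gap to matter in either direction; the check is what would show it.

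A second defence is that deferred doses should be given within 14 days. That rule names #2, #3 and #4 alike, so it cannot justify leaving out only #4. It does bear on size: if it governs and was followed, no #4 is more than 14 days late.

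Third, SAP 4.1 refers to protocol section 10.7.1, which is not in the text available. A timing condition there cannot be ruled out, although both SAP descriptions of the set carry none.

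A reader might also infer that excluding #2 and #3 is misdirected, since SAP 4.3 broadens neither visit. That does not follow. Protocol 6.2.3 broadens post-entry visits generally, so those doses could have been delayed too, and keeping them in the exclusion is right.

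**Conclusion.** The gap in scope is real and minor. The single COVID-19 check covers two of the three doses that could be delayed and omits the one whose broadened window the SAP states. An unchanged result would support robustness to delay of #2 and #3 only.

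Two stronger readings are tempting and not supported. One is that the primary result is compromised: its population, test and alpha do not depend on this bullet. The other is that #4 was in fact given months late. The documents give neither the number of late #4 doses nor the direction of any effect. The 77-day figure assumes that week 48 is the next visit, that the midpoint rule applies and that the two-week interval to the sample is kept. It falls to 14 days or less if there is a visit at week 30 or earlier, or if the 14-day deferral rule governs. It rises if the [22, 50] window overrides the midpoint rule, and the SAP does not say how the two fit together.

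**What to change.** In the third sensitivity bullet of SAP 5.1, insert #4 so that the list reads #2, #3 and/or #4, and leave the rest as it stands. Do not add a more-than-14-days threshold. The present bullet has none, so a threshold would return to the set participants with shorter #2 or #3 delays who are now excluded, and it would exclude nobody if the deferral rule was followed.

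Report by arm the number excluded and the actual #3-to-#4 and #4-to-sample intervals. If #4 was left out on purpose, state the reason and still report the intervals.

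The cost is one edited bullet, one short table and a rerun of a planned analysis. The bullet already requires pandemic delays to be identified for #2 and #3; the same has to be done for #4. The downside is a smaller set, with each exclusion taking 5.6% or 11.1% of an arm of 18 or 9. It should therefore be read on the Hodges-Lehmann estimate and its confidence interval, not on the p-value.

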5.2 Analysis of the Primary Safety Objective

All participants who have been exposed to the study treatment will be included in modified intent-to-treat analysis. The primary safety outcome will be summarized separately by treatment arm, including the number and percentage of participants experiencing a primary safety outcome with an exact binomial 95% CI.

All primary safety outcome records will be listed along with AE grade, diagnosis time, vaccination time, and relationship to study treatment.

5.3 Analysis of the Secondary Objectives

The percentage of participants in each study arm with a CD4 and/or CD8 cell response to an increased number of CEs at week 26 compared to baseline will be presented along with an exact binomial 95% CI. Pairwise comparisons among study arms will be conducted using Fisher's exact test. Similar analyses will be performed for CD4 and CD8 cell responses separately.

The absolute change in total magnitude of CD4 T cell responses against each CE added together among study arms will be compared using the two-sided Wilcoxon rank-sum test. The analysis for CD8 T cell responses will be conducted in the same manner. All statistical tests will be two-sided at the 5% nominal level of significance without adjustment for multiple testing.

6 Report components

Detailed descriptions of the content of each of the following sections are given in the AIP.

1. Study entry
 - a. Screening
 - b. Accrual
 - c. Eligibility and stratification errors
2. Baseline characteristics
3. Protocol deviations
4. Study and treatment status
5. Primary immunogenicity outcome
 - a. Evaluability
 - b. Primary immunogenicity outcome
 - c. Sensitivity analyses
6. Safety:
 - a. Primary safety outcome
 - b. Deaths
 - c. Overall safety
7. Secondary Outcomes

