2.1 Study Design

A5369 is a phase I/IIa, randomized, double-blind, placebo-controlled study that will evaluate the safety, immunogenicity, and preliminary assessment of efficacy of a novel vaccine encoding “conserved elements” (CE) of the HIV-1 Gag core protein, p24Gag, as a therapeutic vaccine in HIV-1 infected persons on antiretroviral therapy (ART) with the aim to induce potent virus-specific cytotoxic T lymphocytes (CTL) responses. The primary efficacy outcome will be based on HIV-specific immunologic assays at baseline and week 26.

Duration

Participants will be on study for a total of 48 weeks.

Sample Size The target sample size of 40 (20 p24CE; 10 full length Gag; 10 placebo) for the randomized arms is selected to detect a 0.54 difference in the probability that a participant has increased CE responses (0.64 for p24CE vaccine and 0.10 for placebo) between arms based on a two-sided Fisher's exact test with 80% power, 5% alpha level, and 10% inflation of the estimated sample size for loss-to-follow-up or unusable laboratory specimens. The study also has approximately 80% power to detect a difference of 0.85 versus 0.30 when comparing the p24CE and full-length Gag vaccine arms.

Population

HIV-infected individuals receiving ART with plasma HIV-1 RNA <50 copies/mL for at least 2 years (one “blip” allowed), current CD4 T cell counts >500 cells/mm³, and nadir CD4 T cell counts >350 cells/mm³ (by documentation or candidate recall).

Randomization and Stratification

Participants will be randomized 2:1:1 to the p24CE/full-length Gag DNA vaccine arm versus full-length Gag DNA vaccine arm versus placebo arm using the permuted block method.

Randomization will be stratified by indication of willingness to have the leukapheresis procedure at study screening. The active vaccines/placebo will be administered by intramuscular injection/electroporation.

Regimen

Arm 1: p24CE/full-length Gag DNA Vaccine Arm

p24CE1/2 pDNA 4 mg administered by injection/electroporation at week 0 and week 4. Then p24CE1/2 pDNA 2 mg admixed with full-length p55gag pDNA 2 mg administered by one injection/electroporation at week 12 and week 24.

Arm 2: Full-length Gag DNA Vaccine Arm

Full-length p55gag pDNA 4 mg administered by one injection/electroporation at week 0, week 4, week 12 and week 24

Arm 3: Placebo Arm

Placebo (Sodium Chloride for Injection, USP 0.9%) 1 ml administered by one injection/electroporation at week 0, week 4, week 12 and week 24.

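### A small, cheap efficiency gain, not an error: Boschloo's exact test could replace Fisher's for the secondary percentages with an increased CE count, if its ordering statistic is fixed before unblinding

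*SAP*

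**What the plan says.** SAP 5.3 reports, by arm, the percentage of participants whose number of recognised CEs rises from baseline to week 26, with an exact binomial interval for each arm. It then says "Pairwise comparisons among study arms will be conducted using" Fisher's exact test, and repeats this for CD4 and CD8 responses separately. Each test is two-sided at a nominal 5%, with no adjustment for multiplicity. No mid-p or unconditional exact test is mentioned, and no interval for the difference between arms is given for these percentages.

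The same binary outcome and the same test carry the sample size in SAP 2.1: "The target sample size of 40 (20 p24CE; 10 full length Gag; 10 placebo) for the randomized arms", based on a "two-sided Fisher's exact test with 80% power, 5% alpha level", with assumed rates of "0.64 for p24CE vaccine and 0.10 for placebo" and "10% inflation of the estimated sample size for loss-to-follow-up or unusable laboratory specimens". A second contrast is stated to have "approximately 80% power to detect a difference of 0.85 versus 0.30 when comparing the p24CE and full-length Gag vaccine arms". SAP 5.1 confirms that power was calculated on the binary outcome. It makes the primary analysis a Wilcoxon rank-sum test on the change in CE count, expected to be more powerful.

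**The concern.** Fisher's test conditions on the total number of responders. In small arms, few tables are possible for each total, so the attainable significance levels are coarse. The largest attainable level at or below 5% can be far below it. The unused part of the 5% is lost power.

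Exact unconditional tests avoid part of this loss. They maximise the rejection probability over the unknown common response rate instead of fixing the margin. Boschloo's test uses Fisher's p-value only to rank the tables. It therefore keeps the error at or below 5% and is never less powerful than the Fisher test on which it is built.

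At stake is power for the secondary comparisons of percentages: three pairs of arms by three response definitions, or nine tests. A result such as 4/9 v 0/9 can fall on either side of 5% depending on which of two valid exact tests the SAP names.

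**Working it through.** **Inputs**
- Randomised: 20, 10 and 10 (SAP 2.1, ratio 2:1:1).
- Evaluable after the planned 10% allowance: 20 × 0.9 = 18 and 10 × 0.9 = 9, so 18:9:9. In reverse, 36 / 0.9 = 40.
- Rates: 0.64 v 0.10 (p24CE v placebo) and 0.85 v 0.30 (p24CE v full-length Gag), both from SAP 2.1.
- Level: two-sided 5% per test (SAP 5.3).
- Assumptions: the documents give no rates for Gag v placebo. The 9 v 9 rows therefore borrow either 0.64 v 0.10, or 0.30 v 0.10 (one rate from each stated pair). The 16 v 8 row assumes 20% loss, twice the planned allowance.

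**Method**
1. For responders x of n1 and y of n2, compute Fisher's two-sided p, P_F(x,y): the sum of the hypergeometric probabilities, given x + y, that do not exceed that of the observed table.
2. Fisher rejects when P_F ≤ 0.05.
3. Power at (p1, p2) = Σ Bin(x; n1, p1) · Bin(y; n2, p2) over the rejected tables.
4. True size = the maximum of the same sum with p1 = p2 = θ, over a fine grid of θ from 0.0005 to 0.9995.
5. Boschloo's p for a table = the maximum over θ of Pr(P_F ≤ observed P_F). It rejects when this is ≤ 0.05.

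**The plan's own figure.** At 18 v 9, Fisher's power is 79.8% for 0.64 v 0.10 and 79.4% for 0.85 v 0.30. Both reproduce the stated 80% and approximately 80%.

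**True size (maximum over θ)**

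| Arms | Fisher | Boschloo |
|---|---|---|
| 18 v 9 | 3.9% | 4.8% |
| 9 v 9 | 2.1% | 3.3% |
| 16 v 8 (assumed) | 2.8% | 4.8% |

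At a common rate of 0.10, the SAP's assumed placebo rate, Fisher's size is 1.1% at 18 v 9 and 0.07% at 9 v 9.

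**Power**

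| Arms | Rates | Fisher | Boschloo | Gain (points) | Basis |
|---|---|---|---|---|---|
| 18 v 9 | 0.64 v 0.10 | 79.8% | 80.8% | 1.0 | SAP 2.1 |
| 18 v 9 | 0.85 v 0.30 | 79.4% | 83.5% | 4.1 | SAP 2.1 |
| 9 v 9 | 0.64 v 0.10 | 56.4% | 64.9% | 8.5 | assumed rates |
| 9 v 9 | 0.30 v 0.10 | 4.8% | 11.6% | 6.7 | assumed rates |
| 16 v 8 | 0.64 v 0.10 | 68.8% | 78.3% | 9.5 | assumed loss |

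Gains are taken before rounding.

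If nobody is lost, the gains at 20 v 10 are 4.5 points (0.64 v 0.10) and 1.6 points (0.85 v 0.30). At 10 v 10, Fisher's maximum size is 1.3%, and with the borrowed rate pairs 0.64 v 0.10 and 0.85 v 0.30 the gains are 17.8 and 18.6 points. The gain is not steady: at 20 v 10 with 0.30 v 0.10 it is essentially nil (9.8% either way).

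**Single-table example, 4/9 v 0/9.** Fisher's one tail is C(9,4)/C(18,4) = 126/3060 = 0.041. The opposite table is equally likely, so the two-sided p is 0.082. Boschloo's p is 0.033.

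**Sensitivity to the convention.** Some software forms the two-sided Boschloo p as twice the smaller one-sided p. At 18 v 9 this gives 80.6% for 0.64 v 0.10 and 79.4% for 0.85 v 0.30, so the second gain disappears. Individual tables can change sides:
- 15/18 v 4/9: p = 0.048 when ordered by Fisher's two-sided p, and 0.051 by doubling.
- 6/18 v 0/9: 0.040 and 0.058.

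At 9 v 9 the two conventions give the same power. Both rejection regions contained Fisher's at every arm size checked.

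**The case against.** The strongest reply is that nothing is wrong. Fisher's test is valid and pre-specified, and it matches the sizing text. The stated 80% already includes its conservatism, so no promised power is lost. This stands: the point is a preference between two valid exact tests, justified only by power. A reader might infer from the low true size that the trial is underpowered or its sample size miscalculated. The documents do not support that, because the stated power reproduces with Fisher's test.

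It can also be said that SAP 5.1 already answers the inefficiency of the binary outcome by making a Wilcoxon test on the CE change primary. That stands too. Because the trial was sized on this percentage, a reader might infer that the main inference is affected; it is not.

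The larger gains rest on rates or losses that the plan does not set. SAP 2.1 plans for 10% loss, and SAP 5.1 expects little missing data. For Gag v placebo at 0.30 v 0.10, power is very low with either test. A reader might infer a general gain of up to 10 points, but for the contrast that set the sample size it is 1.0 point at 18 v 9.

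Finally, with nine unadjusted tests, Fisher's conservatism acts as an incidental brake on false positives. Boschloo's test releases part of it. This is a real trade-off, but each test still respects the nominal 5% that SAP 5.3 sets. None of these replies removes the gain; they limit its size and importance.

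**Conclusion.** The point holds as an optional improvement to a secondary analysis. With Fisher's two-sided p as the ordering statistic, Boschloo's test adds 1.0 point of power for p24CE v placebo and 4.1 points for p24CE v Gag, at the design rates and 18 v 9 evaluable. It rejected whenever Fisher's test did at every arm size checked, and its size stays below 5%. The figures of 8.5 and 6.7 points (9 v 9) and 9.5 points (16 v 8) are conditional on the assumptions labelled above. All figures assume independent binomial outcomes. The 18:9:9 split is inferred from the 10% inflation; SAP 5.3 does not name an analysis population for these percentages, so the numbers actually compared may differ.

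**What to change.** In SAP 5.3, before unblinding:
- Name Boschloo's two-sided exact unconditional test for the between-arm percentages (CD4 and/or CD8, CD4, CD8), with Fisher's two-sided p-value as the ordering statistic and maximisation over the common rate.
- Name the software and version, and check it on a known table. At 18 v 9, 15/18 v 4/9 should give 0.048, not 0.051.
- Report Fisher's p-value as supportive, since the sample-size text uses it.
- If a confidence interval for the difference in percentages is added, specify its test statistic and inversion method. Agreement between the interval and the test should not be assumed.

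The cost is a few sentences and a code check. The downsides are a less familiar test, a convention that can change a borderline result if left open, and unadjusted secondary tests that each use more of their nominal 5% (maximum size from 3.9% to 4.8% at 18 v 9, and from 2.1% to 3.3% at 9 v 9). The sample size and the primary analysis need no change.

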3.2 Secondary Outcome Measures

Per protocol Section 10.2.1, the secondary outcome measures are as follows:

1. The number of CEs with a CD4 T cell response at week 26 compared to baseline in an individual study participant.
2. The number of CEs with a CD8 T cell response at week 26 compared to baseline in an individual study participant.
3. The total magnitude of CD4 T cell responses against each CE added together in each study arm at week 26 compared to baseline.
4. The total magnitude of CD8 T cell responses against each CE added together in each study arm at week 26 compared to baseline.

4 Statistical Principles

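### The CD4 and CD8 magnitude comparisons use baseline only by subtraction; a pre-specified rank ANCOVA on baseline would gain precision in arms this small unless baseline and week 26 are highly correlated

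*SAP*

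**What the plan says.** SAP section 3.2 defines the third secondary outcome as "The total magnitude of CD4 T cell responses against each CE added together in each study arm at week 26 compared to baseline", and the fourth is its CD8 counterpart. Section 5.3 turns this into an analysis of week 26 minus baseline: "The absolute change in total magnitude of CD4 T cell responses against each CE added together among study arms will be compared". The same sentence names the method, saying that these changes "will be compared using the two-sided Wilcoxon rank-sum test". For CD8 it adds: "The analysis for CD8 T cell responses will be conducted in the same manner". On error control: "All statistical tests will be two-sided at the 5% nominal level of significance without adjustment for multiple testing".

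For these two outcomes section 5.3 states no baseline covariate, no transformation, and no effect estimate or confidence interval. The SAP's only covariate-adjusted analysis is the Van Elteren test in section 5.1. It is a sensitivity analysis for the primary count outcome, and it adjusts for the randomization stratum, not for baseline response. The stratum is described in section 2.1: "Randomization will be stratified by indication of willingness to have the leukapheresis procedure at study screening".

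**The concern.** Subtracting baseline fixes its coefficient at 1. With equal SDs at the two visits, the best coefficient is the baseline to week 26 correlation, rho. When rho is well below 1, subtraction over-corrects and leaves regression to the mean in the change score. An arm that by chance starts high then tends to show a smaller change, and an arm that starts low a larger one.

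Summed response magnitudes are bounded at zero and are likely to be right-skewed. On the raw scale, participants with large baseline responses therefore tend to take the extreme ranks of change in both directions, which adds noise.

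At stake are precision and power for secondary objectives 4 and 5. The arms are small enough that sizeable baseline imbalance is common. Baseline magnitude is already measured, since the change cannot be computed without it.

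**Working it through.** **Inputs from the documents.** Section 2.1 gives 40 randomized (20, 10 and 10), 10% inflation for loss, and design rates of "0.64 for p24CE vaccine and 0.10 for placebo". Section 5.3 gives the rank-sum test at two-sided 5%. No power, SD, distribution or correlation is given for the magnitude outcomes.

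**The plan's own figure.** 20 × 0.9 = 18 and 10 × 0.9 = 9. Exact enumeration of the two-sided Fisher test at 18 v 9 gives power of 79.8% for 0.64 v 0.10 and 79.4% for 0.85 v 0.30. The stated 80% reproduces for both. This sets the evaluable numbers: 18 v 9 for p24CE against either other arm, and 9 v 9 for full-length Gag against placebo.

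**Variance by formula (equal SDs).** Change-score variance is proportional to 2(1 − rho) and ANCOVA variance to 1 − rho², so the ratio of ANCOVA to change is (1 + rho)/2.

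| rho (assumed) | ANCOVA / change | change / ANCOVA |
|---|---|---|
| 0.3 | 0.65 | 1.54 |
| 0.5 | 0.75 | 1.33 |
| 0.7 | 0.85 | 1.18 |
| 0.9 | 0.95 | 1.05 |

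Estimating one extra coefficient with 27 participants multiplies the ANCOVA variance by about 1 + 1/23. At rho 0.9 this gives 0.95 × 1.043 = 0.99, so the gain has gone.

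**Power by simulation.** Assumptions: log-normal baseline and week 26, log SD 1, vaccine effect of 1 SD on the log scale.

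| rho | 18 v 9: planned Wilcoxon | 18 v 9: rank ANCOVA | 9 v 9: planned Wilcoxon | 9 v 9: rank ANCOVA |
|---|---|---|---|---|
| 0.3 | 53% | 65% | 37% | 50% |
| 0.5 | 64% | 72% | 48% | 56% |
| 0.7 | 82% | 84% | 67% | 70% |
| 0.85 | 97% | 98% | 88% | 88% |

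Repeat runs at 18 v 9 agreed within about 2 points. At rho 0.9 both methods gave about 99%. Null rejection was 4.2% to 5.5% for the planned test and 4.7% to 5.9% for rank ANCOVA.

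With an additive effect instead (assumed at 1.5 times the baseline median, 18 v 9), power was 59% v 82%, 72% v 86%, 84% v 93% and 95% v 98% at the same four correlations.

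**Chance imbalance.** The standard error of the difference in mean log baseline, in SD units, is √(1/18 + 1/9) = 0.408. A difference above 0.5 SD lies beyond 0.5/0.408 = 1.22 standard errors, which happens in 22% of trials. At 9 v 9 it is √(2/9) = 0.471 and 0.5/0.471 = 1.06, so 29%. On the log scale, an imbalance of 0.5 SD shifts the expected difference in change by −(1 − rho) × 0.5: −0.35 SD at rho 0.3, −0.25 at 0.5 and −0.15 at 0.7.

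Among null 18 v 9 trials with imbalance above 0.5 SD, rejection rates were:

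| rho | Planned Wilcoxon | Rank ANCOVA |
|---|---|---|
| 0.3 | 10.3% | 3.9% |
| 0.5 | 9.5% | 4.5% |
| 0.7 | 6.6% | 3.6% |

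With a true effect at rho 0.3, power was 32% v 62% when the vaccine arm started more than 0.5 SD higher, and 75% v 56% when it started more than 0.5 SD lower. The planned test moves with the imbalance; rank ANCOVA much less so.

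**Influence of single values.** In one simulated data set the largest change was multiplied by 10 and then by 100. The Wilcoxon p-value (0.208) and the Hodges-Lehmann estimate (0.52) did not move. The mean difference went from 0.37 to 1.59 and then 13.83.

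**The case against.** The planned analysis is valid under randomization. Regression to the mean adds variance and does not bias the test over repeated trials. This stands: the point concerns efficiency and sensitivity to imbalance, and the plan contains no error here.

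A reader might infer that a few high-baseline participants could drive the result. The documents do not support that, because the sentence that defines the change also specifies a rank-sum test, under which an extreme change counts only by its rank. Nor is it right to say that baseline is ignored, since it is subtracted.

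The planned method also matches secondary objectives 4 and 5, which are worded as comparisons of change, and it mirrors the primary analysis in section 5.1. Absolute change is on the assay scale and easy to read, whereas Quade's method gives a p-value on ranked residuals with no estimate in assay units. This is a good reason to keep the change analysis beside the adjusted one. It does not argue against adding the adjusted one, because under randomization both test for an effect of vaccine on week 26 magnitude.

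The size of the gain rests on an assumed shape, SD, effect and correlation. That stands too. The direction held for multiplicative and additive effects, but the gain under the multiplicative effect is at most about 1 point at rho 0.85.

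The stakes are modest: two of four secondary outcomes in what section 5.1 calls a pilot study. The Analysis Implementation Plan, which is not among the documents, might add detail. The SAP's introductory text gives it table and figure outlines and coding descriptions, so the choice of method belongs in section 5.3.

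**Conclusion.** The point holds as an efficiency improvement for two secondary outcomes. Section 5.3 plans a valid comparison that uses baseline only by subtraction. Under the assumed log-normal model at 18 v 9, a baseline covariate adds about 12 points of power at correlation 0.3, 8 at 0.5 and 2 at 0.7, and nothing material from 0.85 up. The gains at 9 v 9 are similar (13, 8 and 3 points). In the roughly one trial in five (18 v 9) or three in ten (9 v 9) with baseline imbalance above 0.5 SD, the planned result tends to follow that imbalance when the correlation is low or moderate. The documents give neither correlation nor SD, so these are ranges under stated assumptions and not estimates for this trial.

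Two further inferences should be resisted: that the planned test has inflated overall type I error (it was about 5%), and that every form of adjustment is free. Adding the leukapheresis stratum when it is not prognostic cost about 1 to 4 points of power.

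**What to change.** In section 5.3, before treatment codes are opened:

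- Pre-specify a rank-based ANCOVA (Quade) of week 26 total magnitude on baseline total magnitude for each pairwise arm comparison, separately for CD4 and CD8. Ranks need no log transformation, so zero values cause no difficulty.
- Keep the planned Wilcoxon test on absolute change, and report it with a Hodges-Lehmann estimate and confidence interval, as section 5.1 already does for the primary outcome.
- State in advance which p-value leads, so that the choice cannot follow the results. The rank ANCOVA is the natural one, since the gain lies there.
- Use the leukapheresis-willingness stratum only as a sensitivity adjustment.

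The cost is a few lines of SAP text and code, on data already collected. There are two small downsides: the rank ANCOVA p-value carries no effect estimate in assay units, which the retained change analysis supplies, and nothing is gained if the baseline correlation turns out to be very high.
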